4.4 End of Study Definition

An interventional participant is considered to have completed the study if they have completed all phases of the study, including the visit at 10 weeks postpartum or at 10 weeks from the date of the pregnancy terminating event (ie, abortion [spontaneous/elective] or stillbirth). A child born during the study will have completed after the 12-month visit has been completed.

A non-interventional (observational) sub-study participant is considered to have completed the study if they have completed all phases of the study, including the visit at 10 weeks postpartum or at 10 weeks from the date of the pregnancy terminating event (ie, abortion [spontaneous/elective] or stillbirth).

The end of the study is defined as the date of the last visit of the last participant in the study or last scheduled procedure shown in the schedule of activities (SoA [Section 1.3]) for the last participant in the trial (globally).

5 STUDY POPULATION

Prospective approval of protocol deviations to recruitment and enrollment criteria, also known as protocol waivers or exemptions, is not permitted.

Eligibility for this study will be established using a two-part screening procedure. Screening Part 1 will identify those participants who are at higher risk for the occurrence of maternal HPA-1a alloimmunization and FNAIT in their pregnancy. If a participant meets eligibility criteria in Screening Part 1, they may proceed to Screening Part 2 to determine their eligibility for enrollment and subsequent treatment with RLYB212.

Eligibility criteria are provided in [Section 5.1](#) and [Section 5.2](#).

Approximately 5,000 participants will be screened to identify 8 pregnant individuals who meet the study-specific blood test results required for study inclusion and for whom the pregnancy results in a live birth and who are evaluable for PK and safety assessments. Women in their first or subsequent pregnancy may be included in the study. These participants will be HPA-1b/b and HLA-DRB3*01:01 positive genotype, anti-HPA-1a alloantibody negative, and fetal HPA-1a/b positive.

5.1 Eligibility Criteria for Screening (Part 1)

The following criteria will be assessed.

5.1.1 *Inclusion Criteria to be Confirmed at Screening Part 1*

1. Written/signed informed consent (for Screening Part 1)
2. 18-45 years of age
3. Pregnant women who present at GW 6 or after and confirmed to be:
 - a. HPA-1b/b (HPA-1a negative)
 - b. HLA-DRB3*01:01 positive
 - c. Anti-HPA-1a alloantibody negative
 - d. Carrying an HPA-1a/b (HPA-1a positive) fetus

5.1.2 *Exclusion Criteria to be Confirmed for Screening Part 1*

1. Prior history of HPA-1a-related FNAIT
2. Prior history of HPA-1a alloimmunization
3. Prior history of platelet transfusion or other blood transfusions
4. $BMI \geq 35 \text{ kg/m}^2$

5.2 Eligibility Criteria for Study Intervention

Participants who meet all eligibility criteria in Screening Part 1 (ie, HPA-1b/b, HLA-DRB3*01:01 positive genotype; anti-HPA-1a alloantibody negative; fetal HPA-1a/b genotype) and who provide informed consent for Screening Part 2, will be assessed for eligibility to enter the study's antenatal treatment phase and to receive treatment with RLYB212 provided all inclusion and no exclusion criteria are met. If a participant is eligible for the intervention (Screening Part 2), but the current cohort has been fully enrolled, the participant will be requested to consent for enrollment in the non-interventional (observational) sub-study.

5.2.1 *Inclusion Criteria for Study Drug Administration to be Confirmed at Screening Part 2*

1. Written/signed informed consent (for Screening Part 2)
2. 18-45 years of age
3. Pregnancy no later than GW 16 at the time of first study drug administration as determined by the principal investigator or qualified staff

5.2.2 *Exclusion Criteria for Study Drug Administration to be Confirmed at Screening Part 2*

Participants are excluded from the study if any of the following criteria apply:

1. Multiple pregnancy (>1 fetus)
2. Known sensitivity and/or immediate hypersensitivity to any components of RLYB212 or its formulation
3. History of hypersensitivity to protein therapeutics
4. Any participant with a history of past or current intravenous immunoglobulin (IVIG) use for an underlying disease (eg, autoimmune disease)
5. Requires ongoing systemic corticosteroid or systemic immunosuppressive treatment for any reason
6. History of pre-eclampsia in a previous pregnancy
7. Participants with an in vitro fertilized pregnancy or serving as pregnancy surrogates
8. Current (or within the last 90 days) participation in another clinical study and have received an investigational drug and device within the last 90 days
9. Participants known or suspected of not being able to comply with this study protocol
10. History of any connective tissue or autoimmune or autoinflammatory disease, especially autoimmune thrombocytopenia

11. Any co-morbid medical or obstetric condition(s), laboratory abnormality, concomitant treatment, or other reason that, in the investigator's opinion, could adversely affect the safety of the participant and/or fetus, impair the assessment of study results, or preclude compliance with the study

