6.6 Concomitant Therapy

Standard treatments given during obstetric care are allowed. Routine vaccines, given at recommended times during or immediately after pregnancy, will be allowed in the study.

Any medication (including over-the-counter or prescription medicines, vitamins, and/or herbal supplements) or other specific categories of interest that the participant is receiving at the time of enrollment or receives during the study must be recorded along with:

- Reason for use
- Dates of administration including start and end dates
- Dosage information including dose and frequency

The medical monitor should be contacted if there are any questions regarding concomitant or prior therapy.

Concomitant medications may be considered on a case-by-case basis by the investigator in consultation with the medical monitor.

6.6.1 *Rescue Medicine*

There are no rescue medications defined in the protocol.

6.6.2 *Excluded Treatments, Medical Devices, and/or Procedures During Study Period*

Broad spectrum immunosuppressant agents and IVIG are not allowed as concomitant medications with RLYB212 administration. If such treatments are required, RLYB212 will be discontinued but the participant will continue to be followed as described in [Section 7.1](#).

6.7 *Intervention of Overdose or Dosing Errors*

In the event of an error in dosing, including overdose, the investigator should contact the medical monitor/Sponsor immediately and closely monitor the participant for any AE/SAE and laboratory abnormalities. Where available, the quantity of the excess dose as well as the duration of the overdose should be documented. The Sponsor will determine when and if further dosing will be given, and what dose.

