9.2 Sample Size Determination

The primary objectives of the study are to characterize the safety and PK of RLYB212 in HPA-1b/b pregnant women at risk of HPA-1a alloimmunization. Empiric PK data from this study will be used to supplement the parameters for the current clinical pharmacology model, including the impact of target-mediated drug disposition, if necessary. The PK characterization of RLYB212 in this study is intended to be exploratory, rather than to meet a pre-specified statistical objective. The proposed sample size of 8 is consistent with other studies reported in literature intended to characterize the PK of monoclonal antibodies in an exploratory manner and has been determined to be adequate from a PK perspective based on the following:

- *Low to moderate variability observed in RLYB212 PK:* In Study IPA2001 ([Section 2.2.2.2](#)), after a single SC dose of 0.21 mg RLYB212 (n = 6), the CV% for RLYB212 exposure in HPA-1b/b volunteers was 32.2% for C_{max} and 26% for AUC_{last} . After repeat SC dosing in Study IPA2001 (0.29 mg of RLYB212 or placebo on Day 1 followed by 0.1 mg on Days 15, 29, 43, 57, and 71; n = 6), observed CV% were reduced to 18.6% for C_{max} and 18% for AUC_{tau} , respectively, on Day 71. In Study IPA2003 ([Section 2.2.2.2](#)), in HPA-1b/b volunteers who received an HPA-1a positive platelet challenge after single SC doses of 0.09 mg (n = 4) or 0.29 mg (n = 5) RLYB212, the CV% for RLYB212 exposure ranged from 16.5 and 27.2% for C_{max} and from 16 and 24% for AUC_{last} , respectively. Given the low inter-individual variability in RLYB212 PK observed across 4 distinct dose regimens in 21 HPA-1b/b volunteers at dose levels relevant to those proposed in Study IPA2202, including in volunteers receiving antigen-positive platelet challenge, the proposed sample size of n = 8 is adequate for the stated purpose of an exploratory characterization of RLYB212 PK in HPA-1b/b pregnant women at risk of HPA-1a alloimmunization.
- *Antibody PK in pregnancy:* While physiological changes during pregnancy such as increases in body weight and blood volume are well characterized, published data on maternal exposure to therapeutic mAbs throughout the second and third trimesters are available for only a limited number of mAbs to date. [22, 23] While the effect of pregnancy on exposure parameters is mAb-specific, the variability in the reported PK parameters of individual mAbs is modest through all three trimesters of pregnancy.

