2.1. Multiplicity Adjustment

No hypotheses are planned to be formally tested using inferential statistics in this study; hence multiplicity is not a concern.

3. Analysis Sets

For purposes of analysis, the following populations are defined:

Table 1: Analysis sets

Population	Description
Full Analysis Set (FAS)	All participants that fulfill the criteria for screening part 1 and part 2, and received one or more full doses of RLYB212.
Neonate Full Analysis Set (NFAS)	Neonates born to participants that fulfill the criteria for screening part 1 and part 2 and received one or more doses of RLYB212.
Safety Analysis Set (SAS)	All participants in the study who received any dose of RLYB212.
RLYB212 PK Analysis Set	All participants received at least one dose of RLYB212 and at least one RLYB212-PK sample has been analyzed will be included.
Immunogenicity Analysis Set (IMAS)	All participants that fulfill the criteria for screening part 1 and part 2, received one or more doses of RLYB212 and had detection and categorization of ADA.

Population	Description
Alloimmunization Analysis Set (AAS)	All participants who had at least one screening (Screening Part 1 or 2) or baseline (Visit 2) determination of anti-HPA-1a activity and a subsequent determination of anti-HPA-1a activity postpartum.

4. Statistical Analyses

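### Exclusion criterion 8 requires both an investigational drug and a device, so recent exposure to only one of them does not exclude a woman

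*Protocol*

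**What the plan says.** Protocol section 5.2.2 opens its list with "Participants are excluded from the study if any of the following criteria apply", so each criterion stands on its own terms. Criterion 8 reads in full: "Current (or within the last 90 days) participation in another clinical study and have received an investigational drug and device within the last 90 days". The words at issue are "have received an investigational drug and device within the last 90 days". The synopsis repeats the criterion word for word, and neither document restates it differently.

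Three other provisions bear on how it works:

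- Criterion 11 in the same list is a general clause. It covers a "laboratory abnormality, concomitant treatment, or other reason that, in the investigator's opinion, could adversely affect the safety" of the participant or fetus, and also reasons that could impair the assessment of results.
- Protocol section 6.6.2 limits treatment during the study: "Broad spectrum immunosuppressant agents and IVIG are not allowed as concomitant medications with RLYB212 administration". It does not mention investigational products.
- Protocol section 5 states: "Prospective approval of protocol deviations to recruitment and enrollment criteria, also known as protocol waivers or exemptions, is not permitted".

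**The concern.** A 90-day look-back on investigational products is a fixed washout. It is meant to give every site the same answer without judgement. Joining the two product types with 'and' makes the rule apply only to women who received both. Exposure to a drug alone, which bears directly on a PK study, falls outside it.

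The stakes follow from the design. Protocol section 9.2 says: "The primary objectives of the study are to characterize the safety and PK of RLYB212". ADA and neonatal safety are secondary endpoints. There is no control arm against which to judge an adverse event that another agent might have caused. Enrolment is staged as one sentinel, then up to 3, then 4, with DMC review between stages. Protocol section 6.5 lets the regimen for later participants change on PK data from whoever has completed a pregnancy, which may be one woman.

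Eligibility also feeds the analysis sets. SAP section 3 defines the Full Analysis Set as "All participants that fulfill the criteria for screening part 1 and part 2, and received one or more full doses of RLYB212". The neonate and immunogenicity sets carry the same eligibility condition.

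**Working it through.** The plan states no figure on this point, so the check is one of logic and cross-reading.

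**Step 1: the rule as written.** Criterion 8 excludes if A and B and C all hold, where A = participation in another study now or within 90 days, B = investigational drug within 90 days, and C = investigational device within 90 days. The table takes a woman for whom A holds.

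| Exposure within 90 days | As written ('drug and device') | With 'drug and/or device' |
|---|---|---|
| Drug only | not excluded | excluded |
| Device only | not excluded | excluded |
| Both | excluded | excluded |
| Neither (e.g. a natural history study) | not excluded | not excluded |

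The two readings differ only in the first two rows.

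**Step 2: does the list itself support reading 'and' as 'or'?** Criteria 2 and 11 use 'and/or' where either alternative is enough. A reader comparing criteria therefore has a textual reason to take the plain 'and' in criterion 8 at face value.

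**Step 3: does another rule catch the drug-only case?**

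- Criteria 1 to 7, 9 and 10: none mentions investigational products.
- Criterion 11: it could catch her, but it depends on opinion and sets no 90-day period.
- Section 6.6.2: it bars two treatment classes only. Section 6.6 leaves other concomitant medication to case-by-case consideration.
- Section 5: waivers are barred, so the written wording governs.

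**Step 4: effect on the analysis sets.** Under the literal reading, a drug-only woman who meets all other criteria and receives a full dose belongs in the Full Analysis Set. Under the 'and/or' reading she fails eligibility and does not. The Safety and PK sets depend on dosing and sampling, so she is in those either way once dosed and sampled.

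**Step 5: weight of one participant.** Sentinel stage: 1/1 = 100%. First cohort, if filled to 3: 1/3 = 33%. Planned total: 1/8 = 12.5%. These fractions show how much rests on one woman, not how likely the exposure is.

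**The case against.** The strongest reply is that this is a slip and sites will read it sensibly. Nothing suggests that the sponsor meant to admit women with recent drug-only exposure, and the phrase can be taken as naming the two product types covered. That reading is plausible. It does not make the text unambiguous, and with waivers barred the wording has to give every site the same answer.

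The second reply is that safeguards exist, and they deserve credit:

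- Criterion 11 names the relevant harms, and protocol section 6.6 directs questions on prior therapy to the medical monitor.
- PK and ADA samples are taken before the first dose at Visit 3 (protocol Table 1-3).
- SAP section 4.2.1.1 reviews concentrations with dosing, concomitant medication and AE data before any exclusion from the PK set.
- SAP section 4.3.3 separates pre-existing from treatment-emergent ADA.
- Protocol section 7.2 allows replacement for reasons other than clinical safety.

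These reduce the gap. They rely on judgement or act after enrolment, and none restores a fixed washout.

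The third reply is that the scenario is narrow. If gestation is counted from the last menstrual period (an assumption), GW 16 is 112 days, and 112 − 90 = 22 days, about GW 3. For a woman dosed at GW 16, the look-back falls almost wholly within the current pregnancy, where an investigational exposure would be an obvious case for criterion 11. This lowers the likelihood but leaves the wording as it is.

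A reader might infer two stronger conclusions that the documents do not support. One is that the criterion excludes almost nobody; neither document gives a figure on how often trials supply both a drug and a device. The other is that RLYB212 PK or ADA results would be distorted. If a prior antibody is assumed to share RLYB212's half-life of about 25 days, 2^(−30/25) = 44% remains at 30 days and 2^(−90/25) = 8% at 90 days. That shows residual drug, not interference with RLYB212 disposition, its assay or ADA results, and nothing in the documents shows such interference.

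**Conclusion.** Criterion 8 is wrong as written in both places. Taken literally, it does not exclude a woman with recent drug-only or device-only investigational exposure, and only a discretionary clause could. It is most likely a drafting slip, partly mitigated by the safeguards above. It nevertheless removes the fixed 90-day washout for those women in a study where a single sentinel informs the decision to continue.

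The conclusion rests on the literal text and on the absence of any other automatic rule. It needs no assumption about how common such exposure is, which is unknown. No sample size, error rate or stated figure changes.

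The practical effect is now limited. SAP section 4.9 records that the study ended early on PK grounds with one participant enrolled, and that only listings will be produced. Nothing in the documents indicates that this participant had such an exposure, and none should be inferred.

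**What to change.** In protocol section 5.2.2 and in the synopsis, change 'drug and device' in criterion 8 to 'drug and/or device'. Leave the rest of the criterion unchanged. Participation in a non-interventional study without an investigational product then remains permitted. A separate bar on taking part in any interventional study is not needed to cure the defect and would be a new restriction in a trial expecting to screen about 5,000 women for 8.

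The cost is one change of wording in two places. The small downside is that the rare woman with recent drug-only or device-only investigational exposure becomes ineligible. No analysis changes.

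With the study closed, the useful steps are to keep the present wording out of any later protocol and to confirm from the enrolled participant's eligibility record that she had no such exposure. The prior-medication listing alone may not settle this, because protocol section 6.6 requires recording of medication being received at enrolment or during the study, and an earlier product could fall outside that.

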5.3 Lifestyle Considerations

No dietary or lifestyle restrictions are required.

5.4 Screen Failures (Screening Part 2)

Screen failures are defined as participants who consent to participate in the clinical study but do not subsequently receive the study intervention. A minimal set of screen failure information for those failing to meet criteria at Screening Part 1 and Screening Part 2 is required to ensure transparent reporting of screen failure participants to meet the Consolidated Standards of Reporting Trials (CONSORT) publishing requirements and to respond to queries from regulatory authorities. Minimal information includes demography, screen failure details, assessment of eligibility prior to enrollment, and any SAEs.

Pregnant individuals who do not meet the eligibility criteria for RLYB212 administration may not be rescreened during their current pregnancy. However, these individuals will be requested to consent for the non-interventional (observational) sub-study ([Figure 1-1](#) and [Table 1-1](#)).

6 STUDY INTERVENTION

The study intervention, RLYB212, will be administered to participants in accordance with the study protocol.

Refer to the Pharmacy Manual for detailed information regarding the storage, preparation, administration, and destruction of RLYB212.

6.1 Study Intervention(s) Administered

Dose, formulation, and administration instructions for RLYB212 are provided in [Table 6-1](#). Reference is made to [Section 6.5](#) regarding the approach to dose modification within or between cohorts.

Table 6-1 Study Intervention(s) Administered

	RLYB212
Dosage formulation	Vials, each containing 1 mL of RLYB212 (0.2 mg/mL) solution for SC injection
Unit dose strength(s)/dosage level(s) and dosage frequency^a	RLYB212 is to be administered at an initial (loading) dose of 0.12 mg no later than GW 16 followed by maintenance (repeat) doses of 0.06 mg Q4W throughout the pregnancy and with a final 0.06 mg dose within 24 hours (± 24 hours) of parturition.
Route of administration	SC injection using vial and syringe
Dosing instructions	Refer to Pharmacy Manual for details. The participant will be carefully observed during the injection and observed for 1 hour after the administration.
Storage	2 °C to 8 °C (do not freeze)

GW = gestational week; Q4W = every 4 weeks; SC = subcutaneous.

^a Refer to [Section 4.3](#) for justification of dose/dosing frequency.

6.2 Preparation/Handling/Storage/Accountability

The investigator or designee must confirm appropriate temperature and other storage conditions have been maintained during transit for all study materials received and any discrepancies are reported and resolved before use of the study intervention.

Only participants enrolled in the study may receive study intervention and only authorized site staff may supply or administer study intervention. All study intervention must be stored in a secure, environmentally controlled, and monitored (manual or automated) area in accordance with the labeled storage conditions with access limited to the investigator and authorized site staff.

The investigator, institution, or the head of the medical institution (where applicable) is responsible for study intervention accountability, reconciliation, and record maintenance (ie, receipt, reconciliation, and final disposition records). Further guidance and information for the final disposition of unused study interventions are provided in the Pharmacy Manual.

6.3 Measures to Minimize Bias: Randomization and Blinding

This is an open-label study and there is no randomization or blinding.

6.4 Study Intervention Compliance

Participants will be dosed at the site and receive RLYB212 directly from the investigator or designee and will be observed for 1 hour after dosing by the investigator/site staff. The date and time of each dose administered in the clinic will be recorded in the source documents and recorded in the case report form (CRF). The dose of RLYB212 and study participant identification will be confirmed at the time of dosing by a member of the study site staff other than the person administering the study intervention.

6.5 Dose Modification

Modification of the RLYB212 dose regimen may be necessary to ensure steady state concentrations are maintained through pregnancy and parturition between a target lower bound of ~3 ng/mL and a target upper bound of ~10 ng/mL.

Modification of RLYB212 dose/dose frequency may be made within a cohort or between cohorts, based on available PK data from participant(s) with a completed pregnancy. If the Sponsor determines it is necessary to adjust the RLYB212 dose regimen for future participants, the Sponsor will communicate this to the Investigator and study staff.

Dose modifications are not anticipated during the treatment period of an individual participant.

